7. DISCONTINUATION OF STUDY INTERVENTION AND PARTICIPANT DISCONTINUATION/WITHDRAWAL

7.1. Discontinuation of Study Intervention

Participants will receive study treatment for the duration indicated in Section 6.1 as applicable, unless one of the following events occurs earlier:

- Disease progression
- Death
- Unacceptable toxicity (refer to Section 6.6 and subsections)
- Pregnancy (refer to Section 8.3.5 for details)

In addition, study treatment may be permanently discontinued for any of the following reasons:

- Deviation(s) from the protocol or non-compliance with study requirements
- Request of the participant or proxy (withdrawal of consent by participant or proxy)
- Discretion of the investigator
- Participant is lost to follow-up
- Closure or termination of the study

Participants who have disease progression by RECIST v1.1 may continue study treatment up to the protocol specified 35 cycles at the discretion of the Investigator to confirm progression as per iRECIST guidelines. Nevertheless, the consideration to continue study treatment should be balanced by clinical judgment as to whether the participant is clinically stable. Continuation on study treatment is contingent upon the following conditions:

- Absence of clinical signs or symptoms indicating clinically significant disease progression
- ECOG PS has not worsened, or worsening by no more than 1 point from baseline
- Absence of rapid disease progression or threat to vital organs or critical anatomical sites (e.g., CNS metastasis, respiratory failure due to tumor)

- compression, or spinal cord compression) requiring urgent alternative medical intervention.
- No significant, unacceptable, or irreversible toxicities related to study treatment.

All participants who permanently discontinue study treatment for any reason (except consent withdrawn) will have safety assessments at the time of discontinuation and during follow-up as specified in the SoA.

The primary reason study treatment was permanently discontinued must be documented in the participant's medical records and eCRF. If the participant voluntarily discontinues from treatment due to toxicity, 'adverse event (AE)' will be recorded as the primary reason for permanent discontinuation on the eCRF.

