8.3.1. Time Period and Frequency for Collecting AE and SAE Information

- All AESIs and SAEs will be collected from the start of treatment until 90 days after the last dose of study treatment at the time points specified in the SoA (refer to [Appendix 3](#) for details on SAEs). However, any SAEs assessed as related to study participation (e.g., study treatment, protocol-mandated procedures, invasive tests, or change in existing therapy) OR in countries where collection of SAEs regardless of causality is required to be recorded once the participant signs the informed consent form, SAEs will be recorded from the time a participant consents to participate in the study (i.e., signs the informed consent).
 - If subsequent anti-cancer treatment is initiated during the 90-day follow-up period yet <30 days after the date study treatment was discontinued, AESI ad SAEs must continue to be collected until 30 days after last dose of study treatment.
- All AEs will be collected from the start of study treatment until 30 days after the last dose of study treatment at the time points specified in the SoA ([Table 1](#)).
- Medical occurrences that begin before the start of study treatment but after obtaining informed consent will be recorded in the Medical History/Current Medical Conditions section of the CRF and not in the AE section.
- All SAEs will be recorded and reported to the Sponsor or designee immediately and under no circumstance should this exceed 24 hours. The investigator will

submit any updated SAE data to the Sponsor within 24 hours of learning of the event.

- Investigators are not obligated to actively seek AEs or SAEs in former study participants. However, if the investigator learns of any SAE, including a death, at any time after a participant has been discharged from the study, and he/she considers the event to be reasonably related to the study treatment or study participation, the investigator must promptly notify the Sponsor.

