Scenario 2 – non-proportional hazards with delayed separation of OS curve and heavy tail

Scenario 2 assumes the hazard ratio of OS is non-proportional between the GSK3359609 in combination with pembrolizumab and 5FU/platinum chemotherapy arm and the placebo in combination with pembrolizumab and 5FU/platinum chemotherapy arm, with heavy tails for both arms. Specifically, it is assumed that the hazard ratio between the two arms is ~1 for the first 6 months due to potential delayed treatment effect.

A simulation study was performed with piecewise time varying hazard ratio of OS at time intervals shown below:

	0-6 Month	6-12 Month	12-24 Month	After 24 Month
Hazard Ratio	1	0.69	0.52	0.50

The simulation showed the final analysis will be delayed by approximately 2 months compared with the proportional hazard scenario. Under the non-proportional hazard assumption with 410 events at the final analysis, the study provides 90.2% power to demonstrate superiority of OS at the one-sided alpha level of 2.49% at the final analysis. Success for OS at the final analysis approximately corresponds to an observed hazard ratio of 0.81.

Progression-free Survival

The final PFS analysis will be carried out after approximately 470 events have occurred across two arms. The final PFS analysis is expected to occur at approximately 9 months after the last participant is enrolled in the study. With 470 PFS events, the study has 93.1% power to demonstrate superiority in PFS when the true hazard ratio for PFS is 0.62 at type I error rate of 0.01% (one-sided).

The sample size and power calculation of PFS is based on the following assumptions:

1. PFS follows an exponential distribution with a median of 5 months in the placebo in combination with pembrolizumab and platinum-based chemotherapy arm
2. Hazard ratio for PFS between the GSK3359609 in combination with pembrolizumab and platinum-based chemotherapy arm and the placebo in combination with pembrolizumab and platinum-based chemotherapy arm is 0.62
3. Enrollment period of 21 months and a minimum of 8 months follow-up after enrollment completion
4. Yearly dropout rate of 10%

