An overview summary of AEs, including but not limited to, counts and percentages of participants with any AE, AEs related to study intervention, Grade 3+ AEs, Grade 3+ AEs related to study intervention, AEs leading to permanent discontinuation of study intervention, study intervention related AEs leading to permanent discontinuation of study intervention, AEs leading to dose delays, SAEs, SAEs related to study intervention, fatal SAEs, fatal SAEs related to study intervention and AESIs will be produced.

Adverse events will be coded using the standard Medical Dictionary for Regulatory Affairs (the latest MedDRA dictionary version at the time of reporting) and graded by the investigator according to the NCI-CTCAE v5.0 [[NCI, 2017](#)].

A summary of number and percentage of participants with any adverse events by maximum grade will be produced. AEs will be sorted by System Organ Class (SOC) and Preferred term (PT) in descending order. The summary will use the following algorithms for counting the participant:

- **Preferred term row:** Participants experiencing the same AE preferred term several times with different grades will only be counted once with the maximum grade.
- **Any event row:** Each participant with at least one adverse event will be counted only once at the maximum grade no matter how many events they have.

The frequency and percentage of AEs (all grades) will also be summarized and displayed in descending order by PT only.

A separate summary will be provided for study intervention-related AEs by PT and maximum grade. A study intervention-related AE is defined as an AE for which the investigator classifies the possible relationship to study intervention as “Yes”. A worst-case scenario approach will be taken to handle missing relatedness data, i.e. the summary table will include events with the relationship to study intervention as ‘Yes’ or missing.

All SAEs will be tabulated based on the number and percentage of participants who experienced the event by SOC and PT. A separate summary will also be provided for study intervention-related (fatal and non-fatal) SAEs. The summary tables will be displayed by PT.

A study intervention-related SAE is defined as an SAE for which the investigator classifies the relationship to study intervention as “Yes”. A worst-case scenario approach will be taken to handle missing data, i.e. the summary table will include events with the relationship to study intervention as ‘Yes’ or missing.

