4.5.1. Extent of Exposure

Extent of exposure to GSK3359609, Pembrolizumab, 5FU and platinum-based chemotherapy will be summarized separately and overall, for the Safety Set.

The number of study intervention cycles administered will be summarized with mean, median, standard deviation, minimum, and maximum. The number and percentage of participants who received a given number of cycles (<4, 4-6, and >6) will be reported.

Dose intensity (dose delivered per 3 week period on treatment, accounting for delayed or missed doses) will be summarized using mean, median, standard deviation, minimum, and maximum.

Missed doses will be summarized by number of missed doses and reasons for missed dose, if available. Dose delays will be summarized by number of delays, reasons for the delays, and delay duration (days). The mean, standard deviation, median, minimum value, and maximum value will be computed for the duration of delay as well as the number and percentage of the delays ≤ 21 , 22-42, and >42 days.

The duration of exposure to study intervention (days) will be calculated and summarized using mean, median, standard deviation, minimum, and maximum.

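### AE percentages take no account of observation time, which depends partly on progression, so the descriptive comparison of harm between arms can be modestly distorted in either direction

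*SAP*

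**What the plan says.** **Collection windows (Protocol 8.3.1).** "All AEs will be collected from the start of study treatment until 30 days after the last dose of study treatment". For the more serious categories, "All AESIs and SAEs will be collected from the start of treatment until 90 days after the last dose of study treatment". There is an exception: "If subsequent anti-cancer treatment is initiated during the 90-day follow-up period yet <30 days after the date study treatment was discontinued", in which case collection of AESIs and SAEs is required only to 30 days after the last dose.

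**What sets the last dose (Protocol 6.1 and 7.1).** "Participants will receive study treatment for the duration indicated in Section 6.1 as applicable, unless one of the following events occurs earlier". The listed events are progression, death, unacceptable toxicity and pregnancy. The planned maximum is 35 cycles, and the investigator may continue treatment past RECIST progression.

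**How incidence is summarised (SAP 4.3.2).** The overview gives "counts and percentages of participants with any AE, AEs related to study intervention, Grade 3+ AEs", with further rows for SAEs, AESIs, discontinuations and fatal SAEs. The detailed AE tables and the laboratory worst-grade tables (SAP 4.5.5.1) also use numbers and percentages of participants. Each AESI also gets a count of events and, optionally, time to onset.

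**Exposure (SAP 4.5.1).** "The duration of exposure to study intervention (days) will be calculated and summarized using mean, median, standard deviation, minimum, and maximum". Cycles and dose intensity are summarised as well. None of these is linked to AE incidence.

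**Comparison between arms.** Protocol 9.4.2 planned Miettinen and Nurminen differences for safety. SAP 1.1 removes them. The secondary safety objective in SAP 1.2.1 is still worded as a comparison with the placebo arm.

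**The concern.** The collection rule is the same in both arms, but the time it covers is partly an outcome of treatment. The arm that progresses or dies later tends to be watched longer. The 30-day exception can widen the gap for SAEs and AESIs, since starting new therapy soon after stopping is more likely in the arm that progresses sooner. A percentage with at least one event rises with time watched even when the event rate is the same. Two columns of percentages therefore mix the effect of GSK3359609 on event rate with its effect on time under observation. With the difference and its interval gone, those columns are the main comparative safety evidence in the main CSR and in the safety-only final CSR.

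**Working it through.** **Inputs from the documents.** In Protocol 9.2.1, for the control arm, "PFS follows an exponential distribution with a median of 5 months"; the PFS hazard ratio is 0.62 and allocation is 1:1. The cap is 35 × 21 = 735 days, or 24.1 months at 30.44 days per month. The windows add 30 days (0.99 months) or 90 days (2.96 months). The 41% is the INDUCE-1 share with a serious event (Protocol 2.3.1), used as an illustration.

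**Assumptions.** The documents give no AE hazard, data cut-off or observed PFS effect. Assumed here: treatment ends at progression or the cap; the AE hazard is equal in both arms and constant; the control AE percentage is 20%; potential follow-up is either complete or uniform over 0 to 12 months; and the adverse-direction hazard ratio is 1.25.

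**Step 1. Reproduce the plan's PFS figure.** Power = Φ(√470/2 × |ln 0.62| − 3.719) = Φ(5.182 − 3.719) = 92.8%, against 93.1% stated. With 456 events it is 91.7%, against 92% stated. The PFS effect used below is therefore the plan's own.

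**Step 2. Mean observation time with full follow-up.** Mean = (1 − e^(−λC))/λ + tail, with C = 24.1 months.
- Control: λ = ln 2/5 = 0.1386, giving 6.96 + 0.99 = 7.95 months.
- GSK3359609 arm: λ = 0.62 × 0.1386 = 0.0859 (median 5/0.62 = 8.06 months), giving 10.18 + 0.99 = 11.16 months.
- AE ratio 1.40. For SAE/AESI, 9.92 against 13.13 months, ratio 1.32.

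**Step 3. Percentage shown when hazards are equal.** For event hazard h, P = 1 − e^(−h·tail) × [λ/(λ+h) × (1 − e^(−(λ+h)C)) + e^(−(λ+h)C)]. Solve h for the control percentage and apply the same h in the other arm. For 0 to 12 month truncation, each window is cut at a uniform follow-up time and P is averaged by simulation.

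| Follow-up | PFS HR | 20% AE in control reads | 41% SAE in control reads |
|---|---|---|---|
| Uniform 0–12 months | 0.62 | about 22% | about 43% |
| Full 35 cycles | 0.62 | about 27% | about 49% |
| Uniform 0–12 months | 1.25 | about 19% | about 40% |
| Full 35 cycles | 1.25 | about 17% | about 37% |

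At a hazard ratio of 1 there is no distortion. With treatment time cut at a fixed 3 or 6 months and a hazard ratio of 0.62, 20% reads 21.0% or 22.2%.

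**Step 4. Does a single overall rate cure it?** Under a constant hazard, yes: the rate ratio is 1.00 throughout. Chemotherapy lasts six 21-day cycles (18 weeks), however, so events are likely to come early. If the hazard falls to one third after Week 18 (assumed), at a hazard ratio of 0.62:
- Full follow-up: the AE percentage reads 24.1%, and the first-event rate ratio under equal hazards is 0.89.
- 0 to 12 months: the AE percentage reads 21.5%, and the rate ratio is 0.96.
- At a hazard ratio of 1.25 with full follow-up, the rate ratio is 1.06.

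A single overall rate would then err in the opposite direction to the percentage.

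**The case against.** The best defence is that this is an abbreviated report of a terminated study. SAP 1.1 says between-treatment safety differences will not be analysed, so no risk difference or interval remains to be biased. That stands, and it limits the point to descriptive reading. It does not remove it, because the objective is still comparative and readers will compare the columns.

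Four stronger readings are tempting, and the documents do not support them.
- **Any PFS difference passes fully into observation time.** Toxicity, the 35-cycle cap and discretionary treatment past progression also set the last dose.
- **The distortion is the full-follow-up one (27% and 49%).** That needs a hazard ratio of 0.62 through 35 cycles. The letter of 13 April 2021 stopped GSK3359609/placebo for everyone, about 15 months after the original protocol date of 7 January 2020. Participants could then stay on the same backbone in both arms.
- **The SAP offers nothing but crude percentages.** Exposure summaries, AESI event counts and optional AESI onset times let a reader see unequal exposure, although none adjusts incidence. The output specification and the sponsor's data standards, to which the SAP defers, are not available, so a rate table may be planned there.
- **The percentages hide harm because the drug was withdrawn.** The text gives no efficacy or safety reason for the letter. The hazard ratio of 1.25 is only an assumption.

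The front-loading argument also stands. It shrinks the distortion and rules out resting the comparison on one overall rate.

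**Conclusion.** The point holds in limited form. Observation time depends partly on outcome, incidence is planned as participant percentages, and the SAP names no time-adjusted measure. The likely size at an early cut is one to two percentage points: 20% reads about 22% for AEs and 41% about 43% for SAEs, at the planned PFS effect with an assumed 0 to 12 month truncation. The larger figures are an upper illustration. The sign depends on a PFS effect that the documents do not report. All figures assume equal hazards, and treatment ending at progression or the cap; those in the table also assume a constant hazard. The severity is optional to a low-priority recommendation, and no formal safety estimate is affected.

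**What to change.** In SAP 4.3.2, and again for the final CSR safety update:

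1. For the planned overview rows (any AE, Grade 3+ AE, SAE, AESI, AE leading to discontinuation, fatal SAE), add beside each percentage the exposure-adjusted first-event rate by arm with a 95% CI. Person-time runs from first dose to the earliest of first event, end of the Protocol 8.3.1 collection window, death, withdrawal or data cut-off.
2. Split that rate at the end of the six chemotherapy cycles (about Week 18), or instead give cumulative incidence at a common early time point.
3. Footnote the percentages as not adjusted for observation time and to be read with the exposure table in SAP 4.5.1.
4. Do not say that relative harm is to be judged on the single overall rate.

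The cost is one extra table and a footnote, built from dates already collected, with no new data or participants. The downside is that a rate is only approximate where the hazard is not constant, which is why it sits beside the percentages and is split by phase.

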4.4. Tertiary/Exploratory Endpoint(s) Analysis

Due to early study termination, exploratory endpoint analyses will not be performed for the main CSR.

4.5. Other Safety Analyses

The safety analyses will be based on the safety analysis set, unless otherwise specified.

A final CSR at the end of study will contain only key safety analyses and will be conducted after LSLV for the final CSR. Details around which safety outputs will be created for the final CSR will be provided in the OPS.

4.5.1. Extent of Exposure

Extent of exposure to GSK3359609, Pembrolizumab, 5FU and platinum-based chemotherapy will be summarized separately and overall, for the Safety Set.

The number of study intervention cycles administered will be summarized with mean, median, standard deviation, minimum, and maximum. The number and percentage of participants who received a given number of cycles (<4, 4-6, and >6) will be reported.

Dose intensity (dose delivered per 3 week period on treatment, accounting for delayed or missed doses) will be summarized using mean, median, standard deviation, minimum, and maximum.

Missed doses will be summarized by number of missed doses and reasons for missed dose, if available. Dose delays will be summarized by number of delays, reasons for the delays, and delay duration (days). The mean, standard deviation, median, minimum value, and maximum value will be computed for the duration of delay as well as the number and percentage of the delays ≤ 21 , 22-42, and >42 days.

The duration of exposure to study intervention (days) will be calculated and summarized using mean, median, standard deviation, minimum, and maximum.

4.5.2. Deaths

All deaths will be summarized based on the number and percentage of participants. This summary will classify participants by time of death relative to the last dose of medication (>30 days or ≤ 30 days) and analyze the primary cause of death in the order listed in the CRF. The relationship to COVID-19 infection will also be summarised. A supportive listing will be generated to provide participant-specific details on participants who died.

4.5.3. Adverse Events Leading to Discontinuation of Study Treatment and/or Withdrawal from the Study and Other Significant Adverse Events

The following categories of AEs will be summarized separately in descending order of total incidence by PT only and separate supportive listings will be generated with participant level details for those participants:

- AEs leading to discontinuation of study treatment

A listing of all other significant adverse events will be produced.

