Amendment 1	13-Apr-2020	2019N416505_01
Original Protocol	7-Jan-2020	2019N416505_00

Amendment 2: 30-JUN-2021

Overall Rationale for the Amendment: A Dear Investigator Letter (DIL) dated 13-April-2021 was issued requiring the stopping of further screening and the discontinuation of the administration of GSK3359609 (feladilimab) or placebo for all participants on INDUCE-4, effective immediately. Further to the DIL, since all participants have the option to remain on pembrolizumab alone plus 5FU-platinum as study therapy, GSK issued a Protocol Clarification Letter (PCL) dated 28-April-2021 to reduce any unnecessary burden of on treatment and follow up assessments (the PCL did not alter any screening assessments). This protocol amendment is a follow up to the PCL, with a primary intent to only update the SoA; other impacted, relevant sections were also updated accordingly. Additionally, updates were made to management guidelines to align with pembrolizumab IB update.

Section # and Name	Description of Change	Brief Rationale
1.3 Schedule of Activities (SoA)	Assessments related to GSK3359609 (feladilimab) were removed. These include feladilimab/placebo infusions; feladilimab PK collections, immunogenicity, IRR lab panel, plasma collections, PBMC collections, optional biopsy, Patient Reported Outcomes (PROs), Healthcare Resource Utilization (HCRU), prior protocol required disease assessments, follow-up subsequent anticancer therapy and disease assessments, and pembrolizumab second course. Minor clarifications to pembrolizumab dosing and window extension to PE, PS, and vital signs were also added.	Since there will be no further screening into the study and no further dosing of GSK3359609 or placebo, there is no need to collect samples, PROs or efficacy assessments to determine the effect of GSK3359609

Section # and Name	Description of Change	Brief Rationale
6 Study Intervention	Added reference to Schedule of Assessments.	To align with updated SoA.
6.1.1 Duration of Second Course	Removed section.	Second Course will not be administered as subsequent anticancer therapy will not be followed and PFS2 will not be analysed as the study is terminated with no further screening.
6.6.1 General Guidelines for Immune-Related Adverse Events	Added neurological toxicities and exfoliative dermatological conditions as immune-related AEs and updated myocarditis information.	To align with pembrolizumab IB update (Edition 20 March 2021).

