1. INTRODUCTION

The purpose of this SAP is to describe the planned analyses to be included in the Clinical Study Report (CSR). The main CSR will be an abbreviated report including all primary and secondary endpoints. The final CSR will report updated key safety analyses after LSLV.

Additional detail with regards to data handling conventions and the specification of data displays will be provided in the Output and Programming Specification (OPS) document.

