3. ANALYSIS SETS

Analysis Set	Definition / Criteria	Analyses Evaluated
Screened	
 • All participants who sign the ICF 	
 • Study population
Enrolled	
 • All participants who entered the study • Participants who were randomized or dosed in error are included in the enrolled population • Note that screening failures (who never passed screening even if rescreened) and participants screened but not needed (Reserve, Not Used) are excluded from the Enrolled analysis set as they did not enter the study. • This population will be based on the study intervention the participant was randomized to 	
 • Study population

Analysis Set	Definition / Criteria	Analyses Evaluated
Modified Intent-To-Treat (mITT)	
 • All randomized participants whether or not randomized intervention was administered, excluding those who were first dosed or randomized after the date of dear investigator letter (DIL) requesting immediate discontinuation of GSK3359609 /placebo. The date of the DIL is the 13th April. • This analysis set will be based on the study intervention to which the participant was randomized and will be the primary analysis set for the analysis of efficacy data • Any participants who receives a study intervention randomization number will be considered to have been randomized 	
 • Study population • Efficacy
Safety	
 • All randomized participants who take at least 1 dose of study intervention • This population will be the primary population for the analyses of safety data. • Participants will be assigned to the actual study intervention group of GSK3359609 plus pembrolizumab + 5FU-platinum chemotherapy if the participant received any dose of GSK3359609 	
 • Safety • Immunogenicity
COVID-19	
 • All participants in the Safety set who had a confirmed, probable or suspected COVID-19 case diagnosis. 	
 • COVID-19 Assessments

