The number and percentage of participants achieving BOR of CR, PR, SD, PD, NE, as well as those meeting SD durability requirements ($SD \geq 15$ weeks) will be provided separately for the PD-L1 total and $CPS \geq 1$ participants.

The number and percentage of participants achieving ORR and DCR per RECIST v1.1 will be provided separately for the PD-L1 total and $CPS \geq 1$ participants. The 2-sided 95% exact (Clopper-Pearson) confidence limits for the binomial proportion will also be included.

Stratified Miettinen and Nurminen's method will be used for comparison of the ORR/DCR between two treatment groups. The difference in ORR/DCR and its 95% confidence interval from the stratified Miettinen and Nurminen's method with strata weighting by sample size [Chow, 2003] (i.e. where larger strata carry more weight as compared to smaller strata) with a single treatment covariate will be reported separately for the PD-L1 total and $CPS \geq 1$ participants. Participants with unknown or missing response will be treated as non-responders that is these participants will be included in the denominator when calculating the percentage of ORR/DCR.

Duration of Response (DoR) per RECIST v1.1

Duration of response (DoR) per RECIST v1.1 is defined as the time from first documented evidence of CR or PR until first documented disease progression per RECIST v1.1 based upon investigator assessment or death due to any cause, whichever occurs first, among participants who demonstrated CR or PR as the best overall response per RECIST v1.1. Censoring rule will follow those for the primary analysis of PFS per RECIST v1.1.

If the number of participants with a best overall response of CR or PR permits, the Kaplan-Meier method will be used to estimate the survival curves for DoR per RECIST v1.1. The Kaplan-Meier estimates for the median DoR and the first and third quartiles, along with 95% CIs estimated using the [Brookmeyer-Crowley](#) method (1982) will be reported separately for the PD-L1 total and CPS ≥ 1 group by study intervention.

Adverse Events/Serious Adverse Events

The safety analyses will be based on the safety analysis set, unless otherwise specified.

Adverse events analyses including the analysis of adverse events (AEs), Serious AEs (SAEs) and other significant AEs will be based on GSK Core Data Standards.

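### The SAP ties no safety display to the last GSK3359609/placebo infusion, so events long after the April 2021 stop can be pooled with exposure-period events

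*SAP*

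**What the plan says.** **Deaths (SAP 4.5.2).** "All deaths will be summarized based on the number and percentage of participants". Then: "This summary will classify participants by time of death relative to the last dose of medication", with a cut at 30 days. The section does not say which drug's last dose is meant.

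**Adverse events (SAP 4.3.2).** "Adverse events analyses including the analysis of adverse events (AEs), Serious AEs (SAEs) and other significant AEs will be based on GSK Core Data Standards". No on-treatment or treatment-emergent period is defined for the AE, SAE or AESI tables.

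**Safety set (SAP Section 3).** A participant is placed in the GSK3359609 group "if the participant received any dose of GSK3359609". There is no time limit and no cut at the date of the Dear Investigator Letter. The mITT set in the same table does use that date.

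**Collection (Protocol 8.3.1).** "All AEs will be collected from the start of study treatment until 30 days after the last dose of study treatment". For the more serious events: "All AESIs and SAEs will be collected from the start of treatment until 90 days after the last dose of study treatment". Protocol Section 6 allows study treatment to mean either a single drug or the whole combination.

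**After the stop (Protocol, Amendment 2 rationale).** GSK3359609/placebo ended at once for everyone under the letter of 13 April 2021, but "all participants have the option to remain on pembrolizumab alone plus 5FU-platinum as study therapy". The Schedule of Activities still allows pembrolizumab for up to 35 cycles and keeps AE review running.

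**Reporting.** The main CSR comes first. Then: "The final CSR will report updated key safety analyses after LSLV" (SAP Section 1).

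**The concern.** The secondary safety objective is to compare GSK3359609 with placebo on a common backbone. Both arms receive the same drugs once GSK3359609/placebo has stopped. Events after that date say little about the randomised drug, except for delayed effects. As written, nothing in the SAP separates the two periods. A participant with one GSK3359609 infusion before the stop and many months of pembrolizumab afterwards contributes all later AEs to the GSK3359609 column, and the same happens in the placebo column.

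The 30-day death split has a related problem. Its usual purpose is to separate deaths close to treatment from later ones. If the anchor is any study drug, a death soon after a pembrolizumab infusion but many months after the last GSK3359609 infusion falls in the ≤30-day group.

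SAP 1.1 says that between-arm safety differences will not be analysed. Readers will therefore compare percentages side by side, and the counting window decides what those percentages mean. The issue should be largest in the final CSR, after the longest period on the common regimen.

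**Working it through.** **1. The protocol's own duration.** Protocol 6.1 gives about 2 years, up to 35 cycles of 21 days: 35 × 21 = 735 days = 2.01 years. This agrees with the stated figure.

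**2. How far after the last GSK3359609/placebo infusion an event could still be counted.** Assumptions: the last GSK3359609/placebo infusion was on 13 April 2021, later cycles run on schedule, and the anchor is the last dose of any study drug. With *k* further pembrolizumab cycles, the last pembrolizumab dose is 21*k* days later. The AE window and the ≤30-day death category then reach 21*k* + 30 days, and the SAE/AESI window reaches 21*k* + 90 days.

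| Further cycles *k* | 21*k* | AE window, ≤30-day deaths: to day | SAE/AESI window: to day |
|---|---|---|---|
| 1 | 21 | 51 | 111 |
| 6 | 126 | 156 | 216 |
| 12 | 252 | 282 | 342 |
| 34 (maximum) | 714 | 744 | 804 |

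The last row applies only to someone who had their first cycle at the time of the stop and then completed all 35. If the anchor were the last GSK3359609/placebo infusion, the limits would be day 30 and day 90 in every row.

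**3. What pooling does to the contrast.** Let *a*T and *a*C be the risks of a given event in the GSK3359609 and placebo arms during the GSK3359609/placebo window. Let *b* be a later risk that is equal in both arms and independent of the earlier one. The cumulative risk in each arm is p = 1 − (1 − *a*)(1 − *b*), so the risk difference is (*a*T − *a*C)(1 − *b*). It shrinks by the factor (1 − *b*), and the risk ratio moves toward 1.

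Illustration only; the documents give none of these risks:

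| *b* | 30% vs 20%: difference (points) | 30% vs 20%: ratio | 10% vs 5%: ratio |
|---|---|---|---|
| 0 | 10.0 | 1.50 | 2.00 |
| 5% | 9.5 | 1.40 | 1.49 |
| 10% | 9.0 | 1.32 | 1.31 |
| 20% | 8.0 | 1.22 | 1.17 |
| 40% | 6.0 | 1.12 | 1.07 |

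Check of one entry, at *b* = 20%: 1 − 0.7 × 0.8 = 0.44 and 1 − 0.8 × 0.8 = 0.36, so the difference is 8 points and the ratio 1.22.

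**4. Deaths.** Every death is counted under any anchor. Only the allocation to ≤30 or >30 days can change.

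**The case against.** **The SAP does not say any study drug.** This is correct. SAP 4.5.2 leaves the drug unnamed, and the protocol's term is ambiguous by its own definition. A reader might infer that the SAP anchors its AE and AESI tables on the last dose of any drug, or labels these as on-treatment events of the randomised drug. It does neither. The 30- and 90-day limits are protocol collection windows, not display rules. The any-drug reading is plausible because the continuing regimen is called study therapy, but it remains a reading.

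**The rules may exist elsewhere.** The GSK Core Data Standards or the Output and Programming Specification may define a window. Neither is among the documents, and the SAP does not state what they require on this point.

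**The GSK3359609 column cannot look safer over time.** This stands. The planned tables are cumulative counts over a fixed safety set, so percentages can rise or hold but not fall, and no exposure-period event is removed. A reader might infer that toxicity is under-reported, or that the final CSR must look safer than the main one. Neither follows. What can shrink is the contrast between arms.

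**The size is unknown.** This also stands. A rate-ratio estimate based on person-time would need an accrual length and hazards that the documents do not give, and the SAP plans no event rates. Events concentrated in the six chemotherapy cycles would be diluted less. In the earlier GSK3359609 plus pembrolizumab cohort, 94% had at least one AE (Protocol 2.3.1), so the any-AE row may have little room to move. With no data cut-off stated for the main CSR, one also cannot say that the final update would consist almost entirely of post-stop events.

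**Partial safeguards exist.** Exposure is summarised by drug, AEs and deaths are listed, and AESI time to onset may be shown. These allow a reconstruction, but no planned summary isolates the GSK3359609/placebo period.

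**A strict cut could hide late toxicity.** Protocol 6.6.1 notes that immune-related events can appear months after the last dose. This argues for adding window-limited tables, not for replacing the all-event ones.

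**Conclusion.** The point holds as an undefined anchor and a missing display. The documents establish that GSK3359609/placebo stopped for everyone, that the remaining regimen and its event collection continue, that the Safety set has no corresponding cut, and that no summary is limited to the GSK3359609/placebo period.

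The consequence is conditional. If medication and study treatment mean any study drug, pooling can extend to about 744 days after the last GSK3359609/placebo infusion for AEs and the ≤30-day death category, and to about 804 days for SAEs and AESIs. Both are upper limits for a participant who completes all 35 cycles. The pull of the contrast toward the null also requires similar later background risk in the two arms, and its size cannot be derived from the documents.

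This concerns the safety displays only, not the OS or PFS estimands. It is a cheap improvement to the reporting plan.

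**What to change.** - **SAP 4.5.2:** classify deaths by time from the last GSK3359609/placebo infusion, and also by time from the last dose of any study drug, naming the anchor in each display.
- **SAP 4.3.2:** keep the all-event tables. Add AE, SAE and AESI summaries for both arms, limited to onset from first dose to the last GSK3359609/placebo infusion plus 30 days (AEs) or plus 90 days (SAEs and AESIs). Show later events in a separate panel so that late immune-related toxicity stays visible.
- **Both reports:** use the same windows in the main and final CSR.

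The cost is wording in the SAP and the programming specification, plus one extra set of displays. Administration dates are already recorded in the eCRF (Protocol 6.1) and the events are already collected, so no new data are needed. This is a reporting rule and changes no clinical management.
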